		Visit 2	Visit 3 b	Visit 4 b	Visit 5 b	Visit 6	Visit 7	Visit 8 c	Visit 9	Visit 10	
		Day 1	Day 4 (±1 day)	Day 7 (±1 day)	Day 10 (±1 day)	Day 15/ Week 2 (±2 days)	Day 43/ Week 6 (±3 days)	Day 85/ Week 12 (+7 days)	Day 113/ Week 16 (±4 days)	Day 155/ Week 22 (±4 days)	
Ask the subject to complete the WPAI: CRPS u		X						X			
Collect information for medical resources utilization and health economics u		X						X			
Take blood for bone turnover marker evaluation v		X				X	X	X		X	
Take blood for sIL-2R testing		X						X			
Take blood for pharmacogenetic testing w		X									
Take blood for omics testing w		X						X			
Ask the subject to complete the PGIC							X	X	X	X	

a) The Enrollment Period consists of an Enrollment Visit (Visit 1) prior to Day -7 and a baseline pain assessment phase from Day -7 to Day -1 during which subjects will report pain intensity ratings in the electronic diary. These pain intensity ratings will be used to calculate the baseline pain intensity score. Additional visits are allowed during the Enrollment Period to confirm normal laboratory values or ensure protocol targets for vitamin D (for details of repeat testing, see Section 1.3.2). If the Enrollment Period exceeds 30 days, determination of hematology and clinical chemistry parameters should be repeated to confirm there is no major change in the subject's overall health status prior to allocation.

aa) Compliance assessment for electronic diary not required at Visit 1.

b) Infusion visits should be separated by 3-day intervals to the extent possible (i.e., Day 1, Day 4, Day 7, and Day 10). Infusion visits on consecutive days are not allowed. The full dosing period must not exceed 21 days from the first infusion (Visit 2). To facilitate scheduling, the interval between infusion visits may be adapted, provided the 21-day time period is not exceeded and discontinuation criteria can be assessed. In case of suspension of treatment due to a suspected safety concern or a visit scheduling difficulty, resumption of treatment is allowed upon resolution of findings, with sponsor agreement. In case of interruption or suspension of treatment, the first follow-up visit (Visit 6)

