### **7 TRIAL OBJECTIVES AND ENDPOINTS**

The trial objectives and endpoints are given in Section [1.2](#).

The pain intensity score used for the primary endpoint will be calculated from average pain intensity ratings, assessed once daily in the electronic diary and referring to the CRPS-affected limb. The baseline average pain intensity score is defined as the average of the week before allocation to treatment at Visit 2 and calculated as the average of the 7 average pain intensity ratings starting in the evening of Day -7 until Day -1. A baseline pain intensity score ( $\geq 4$  on the NRS) must be confirmed at the site prior to subject allocation (at Visit 2). Subjects who do not meet eligibility criteria due to inadequate pain ( $< 4$  on the NRS) will be excluded from the trial.

Pain intensity scores from Week 1 through Week 12 will be calculated in a similar manner using average pain intensity ratings obtained from the electronic diary. The Week 12 pain intensity score, for evaluation of the primary outcome, will be the average of up to 7 possible ratings obtained in the 7-day period culminating with the rating obtained in the evening prior to the Week 12 visit.

Handling of missing pain ratings will be addressed in the statistical analysis plan. Compliance with the pain ratings in the electronic diary must be monitored and subjects with insufficient ratings ( $< 4$  ratings per week for 2 weeks) should receive a reminder and undergo re-training.

During Visit 2 (Day 1), Visit 7 (Week 6), Visit 8 (Week 12), Visit 9 (Week 16), and Visit 11 (Week 26), Visit 16 (Week 36), and Visit 17 (Week 52), the subjects will be asked to record the pain intensity ratings for average, worst, and current CRPS-related pain directly on a tablet computer maintained at the site. For subjects included in Treatment Period B, the subjects will also be asked to record pain intensity rating at Visit 12, Visit 13, Visit 14, and Visit 15. Worst and average pain intensity ratings will be based on a 24-hour recall period. The pain ratings and other patient-reported outcomes from the tablet computers recorded up to Week 26 as well as DMA, edema, and PPT assessment will be used for the secondary endpoints.

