## **9 SUBJECT ENROLLMENT AND TRIAL DISCONTINUATION**

### **9.1 Subject enrollment procedure**

Subjects will be screened to identify subjects who could potentially be enrolled into the trial. Potentially eligible subjects will be asked to enroll into the trial by giving written informed consent.

If required by applicable regulatory requirements, the (principal) investigator must keep suitable logs of the subject enrollment procedure.

Subjects who were enrolled in KF7013-01 but were not allocated to treatment (i.e., did not receive any treatment with IMP) or who only received placebo may be eligible if they satisfy all inclusion and exclusion criteria in Section 1.3.

Re-enrollment will be permitted (once), upon approval by the sponsor, for subjects with technical reasons for enrollment failure (e.g., inadequate time period for stabilization of treatment; inadequate time from discontinuation of a prohibited medication or treatment). No subject who received infusion of IMP, even a partial infusion, is allowed to be re-enrolled. Re-enrollment of subjects who did not meet inclusion criteria related to the diagnosis of CRPS and the baseline pain level is not allowed. Re-enrolled subjects must fulfill all inclusion and exclusion criteria in the current protocol. If a subject is re-enrolled, a new subject ID will be assigned and all enrollment procedures will be performed under the new subject ID.

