### **11.1.1 Enrollment Period**

The Enrollment Period consists of an Enrollment Visit (Visit 1) from Day -60 to Day -8 and a baseline pain assessment phase from Day -7 to Day -1 during which subjects will record pain intensity ratings in the electronic diary. These pain intensity ratings will be used to calculate the baseline average pain intensity score.

Additional visits are allowed during the Enrollment Period to confirm normalization of laboratory values (e.g., for subjects with vitamin D deficiency, up to a maximum of 4 times repeated laboratory testing for vitamin D in 60 days). For details of repeat testing, see Section [1.3.2](#).

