#### **11.1.1.2 Baseline pain assessment phase (Day -7 to Day -1)**

In order to calculate the baseline pain intensity score, subjects will be asked to rate their average CRPS-related pain intensity using an 11-point NRS once daily (in the evening) during the last 7 days prior to Visit 2, in the electronic diary. Subjects will also be asked to rate their worst and their current CRPS-related pain intensity once daily during the same period of time. The worst and average pain will be based on a 24-hour recall period.

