#### **12.3.1.1 Electronic diary**

Subjects will be asked to record their average, worst, and current CRPS-related pain intensity once daily in the electronic diary (in the evening), using an 11-point NRS (from 0 = “no pain” to 10 = “pain as bad as you can imagine”) starting at Visit 1 and continuing until Visit 8. Worst and average pain intensity will be for a 24-hour recall period.

After Visit 8 up to Visit 17, subjects will be asked to record their average, worst, and current CRPS-related pain intensity once weekly in the electronic diary (in the evening) using the same 11-point NRS and a 24-hour recall period.

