#### *Numerical rating scale for pain*

The unidimensional 11-point NRS is a recommended method of assessing pain intensity in subjects with various types of chronic pain (CPMP/EWP/252/03 Rev. 1).

On the basis of IMMPACT recommendations for core outcome measures in chronic pain studies, the 11-point NRS was chosen as the primary efficacy outcome measure (Dworkin et al. 2005). The NRS is a standard, widely used tool for the assessment of pain (Dworkin et al. 2008). Average, worst, and current pain intensity will be assessed.

For subject-reported outcomes captured electronically, the system will ensure data integrity by allowing only subjects to enter the data (electronic diary, tablet computer at the site). Electronic subject-reported outcome systems ensure that neither sponsors nor investigators can access and change the data, and subjects cannot enter data retrospectively or in advance, i.e., the timing of entries is controlled and compliance is enforced. Additionally, no data are lost because of illegible handwriting. As required by the FDA Guidance for Industry 2009 on the use of subject-reported outcomes, the database for the electronic patient-reported outcomes uses a regular back-up and does not allow access to unblinded data.

Subjects report little difficulty with electronic patient-reported outcome system procedures and are not unduly burdened by their use resulting in good reporting compliance (Stone et al. 2004).

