## **13.2 Subject-reported outcomes**

Subject-reported outcomes will be collected using a validated electronic patient-reported outcome system including audit trail (electronic diary and site tablet computer).

The investigator will be trained on the use of the electronic patient-reported outcome system and the related oversight system. The oversight system will allow the investigator to review all data entered by the respective site subjects on an ongoing basis.

Subjects will receive a personal electronic diary at the trial site and will be instructed on how to use it.

The tablet computers will be kept at the trial site and subjects will be instructed on how to use it.

No queries will be issued to the investigator for these data, except for clarification of subject identifiers and any operational issues. No queries will be raised to the subject.

With database lock, the writing access to the electronic patient-reported outcome system will be removed. The investigator will receive all data captured for his or her subjects, in a human readable form, on read-only media for his or her files. The information will be provided to the investigator prior to system decommissioning.

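### Daily ratings visible to the site from Visit 1, with no Visit 2 date fixed in advance, allow the baseline week to be chosen after the pain is seen; the sections on when rating starts also disagree.

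*Protocol*

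**What the plan says.** The Protocol gives two accounts of when diary rating happens before treatment.

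- Section 1.6.1, footnote a, speaks of "a baseline pain assessment phase from Day -7 to Day -1 during which subjects will report pain intensity ratings in the electronic diary". Section 11.1.1.2 has subjects rate "once daily (in the evening) during the last 7 days prior to Visit 2, in the electronic diary".
- Section 12.3.1.1 has daily rating "starting at Visit 1 and continuing until Visit 8". The diary is handed out and explained at Visit 1 (11.1.1.1).

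The interval is long and flexible: "The Enrollment Period consists of an Enrollment Visit (Visit 1) from Day -60 to Day -8 and a baseline pain assessment phase" (11.1.1). The baseline week is counted back from Visit 2: "The baseline average pain intensity score is defined as the average of the week before allocation to treatment at Visit 2" (Section 7).

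On access, 13.2 states: "The oversight system will allow the investigator to review all data entered by the respective site subjects on an ongoing basis". Section 12.9 says that "neither sponsors nor investigators can access and change the data". In context that sentence is about data integrity, but read as barring access it would contradict 13.2.

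There are three safeguards. A baseline score below 4, checked at Visit 2, excludes the subject. Visit 2 may be rescheduled once for poor diary compliance (1.3.1, criterion 4). Section 9.1 adds: "Re-enrollment of subjects who did not meet inclusion criteria related to the diagnosis of CRPS and the baseline pain level is not allowed".

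**The concern.** The average of the 7 days before Visit 2 decides entry (at least 4 on the NRS). It is also the baseline of the primary endpoint and a covariate in the primary model. It serves these purposes well only if the week is set without knowledge of the ratings in it.

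If ratings accumulate from Visit 1 and the site can read them, the site can watch a running 7-day mean and hold Visit 2 once it reaches 4. The safeguards do not prevent this, because all three act when Visit 2 is reached or failed. Section 9.1 shows that the sponsor does not want second attempts at the pain threshold, yet an open Visit 2 date allows many unrecorded ones. Legitimate delays, such as up to four vitamin D retests in 60 days, mean that a long interval would not stand out.

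At stake are the meaning of the entry threshold, a larger fall from baseline in both arms as selected high weeks revert, and more subjects with little room to improve.

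**Working it through.** **The plan's own figure.** Difference 1.0, SD 2.0, one-sided 2.5%, 90% power (1.5.1). The normal formula gives 85 per arm. The noncentral t gives power 0.8999 at 85 and 0.9032 at 86, so the stated 86 is reproduced. At the planned 90 per arm, power is 91.6% (t) or 91.8% (normal), before any futility look.

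**How many weeks are open.** Visit 1 at Day -60 to Day -8 puts Visit 2 between 8 and 60 days later (no Day 0). That is 60 − 8 + 1 = 53 possible Visit 2 days and 53 overlapping baseline weeks.

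**Chance of qualifying.** The Protocol gives no day-to-day variability, so it is assumed. Daily ratings are simulated as a first-order autoregressive series, rounded and clipped to 0–10, with daily SD 1.2 and lag-1 correlation 0.3. The proportion with a 7-day mean of at least 4 is:

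| Usual pain | Preset week | Any week in 14 days | 28 days | 52 days |
|---|---|---|---|---|
| 3.5 | 23% | 52% | 81% | 96% |
| 3.0 | 6% | 18% | 38% | 61% |

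The any-week columns assume that all seven ratings are seen before booking and that the site uses the choice whenever it can. They are upper bounds. If the last two ratings are still unseen at booking and there is one attempt, the 28-day figure for usual pain 3.5 falls from 81% to about 64%.

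**Sensitivity to the assumptions.** With SD 1.0–1.5 and correlation 0.3–0.8, usual pain 3.5 qualifies in 20–37% of preset weeks, against 75–87% when Visit 2 is chosen among days 8 to 30. For usual pain 3.0 the ranges are 3–22% and 24–66%.

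**Size of the reversion.** When Visit 2 may be chosen among days 8 to 60, the first qualifying baseline exceeds usual pain by 0.6–0.85 points (usual 3.5) or 1.05–1.25 points (usual 3.0). This excess per admitted subject is not created by the free choice: at SD 1.0 and correlation 0.3, usual pain 3.5, it is 0.71 for a preset week and 0.60 when days 8 to 30 are open. What the choice raises is the number of such subjects. Before the threshold is applied, a preset week has no expected inflation (simulated −0.01 to +0.02).

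**Net effect on power.** Assume that the effect is proportional to pain, that other subjects have usual pain 6, and that a share s of those allocated under free choice over 28 days has usual pain 3.5.

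- Mean effect = 1 − share × (1 − 3.5/6) = 1 − 0.4167 × share.
- Share under a preset week: s₀ = s·r / (1 − s + s·r), with r = 0.23/0.81 = 0.284.
- Power = Φ(effect / 0.298 − 1.96), with 0.298 = 2·√(2/90).

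| s | s₀ | Effect, preset | Effect, chosen | Power, preset | Power, chosen | Loss (points) |
|---|---|---|---|---|---|---|
| 10% | 3.1% | 0.987 | 0.958 | 91.2% | 89.5% | 1.7 |
| 20% | 6.6% | 0.972 | 0.917 | 90.3% | 86.7% | 3.6 |

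**The case against.** The strongest reply is that footnote a and 11.1.1.2 describe rating only in the 7 days before Visit 2. On that reading the date must be set before rating begins, and the concern largely goes. This stands as a possible reading but does not settle the matter, because 12.3.1.1 says otherwise. The text needs correcting either way.

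Second, the Visit 2 date is not wholly free. Central laboratory results and a month of stable therapy must be in place. Visit 2 is a fasting visit, and the site should remind the subject 2 days ahead (11.1). A wrong guess excludes the subject. This stands and lowers the figures, as the drop from 81% to about 64% shows. It does not bring them down to 23%, and the reminder is a recommendation, not a requirement (3.2).

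Third, a reader might infer that the Protocol directs sites to choose the week, or that they will. It does neither; it leaves the choice open.

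Fourth, a reader might set the power loss against a trial with no low-pain subjects. That overstates it, because a preset week also admits about 23% of subjects with usual pain 3.5.

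**Conclusion.** The gap holds, as something that the Protocol permits. If rating starts at Visit 1, the site can see a qualifying week before it books Visit 2. That can inflate the baseline and can admit more subjects whose usual pain is below 4.

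A reader might go further and infer a bias towards one arm or an inflated type I error. The documents do not support that. The week is fixed before blinded 1:1 allocation (10.3), and baseline pain is a covariate in the primary model. Regression to the mean falls on both arms alike, and the harm is a larger apparent placebo response and some loss of sensitivity.

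The size is modest: about 2 to 4 points of power as an upper bound. It rests on daily variability, a 10–20% share of low-pain subjects, usual pain 6 in the rest and a proportional effect, none of which the Protocol gives. The point merits action because the same score controls entry and anchors the primary endpoint, and the remedy costs little.

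**What to change.** Either of the first two changes closes most of the gap; both may be made.

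1. In 1.6.1 footnote a and 11.1.1.2, require the Visit 2 date to be recorded in the interactive response system before Day -7. Let it move only for the existing one-time diary-compliance reason or for pending laboratory results.
2. In 13.2, show sites only the number of completed ratings, not their values, until allocation, and have the diary return met or not met at Visit 2. Compliance monitoring continues unchanged.
3. Align 12.3.1.1 with footnote a and 11.1.1.2 on when pre-treatment rating starts, and make the access sentence in 12.9 consistent with 13.2.

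The cost is one date field, a portal display setting and site instructions. Sites lose a little scheduling freedom and, under the second change, the view of pain values before allocation.

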## 3 LIST OF ABBREVIATIONS AND DEFINITION OF TERMS

### 3.1 Abbreviations

Abbreviation	Explanation
β-HCG	Beta-human chorionic gonadotropin
ACR	Albumin to creatinine ratio
ANCOVA	Analysis of covariance
AROM	Active range of motion
BAP	Bone alkaline phosphatase
CKD-EPI	Chronic Kidney Disease Epidemiology Collaboration
COMPACT	Core outcome measures for complex regional pain syndrome clinical trials
CRO	Contract research organization
eCRF	Electronic case report form
CRPS	Complex regional pain syndrome
CRPS-I/CRPS-II	Complex regional pain syndrome Type I/ Complex regional pain syndrome Type II
CTX	C-terminal telopeptide of type I collagen
DMA	Dynamic mechanical allodynia
ECG	Electrocardiogram
EDTA	Ethylenediaminetetraacetic acid
EFPIA	European Federation of Pharmaceutical Industries and Associations
eGFR	Estimated glomerular filtration rate
EMA	European Medicines Agency
EQ-5D-5L	EuroQoL-5 Dimension-5 level

Abbreviation	Explanation
FDA	Food and Drug Administration
GCP	Good clinical practice
IASP	International Association for the Study of Pain
IEC	Independent ethics committee
IL-2	Interleukin-2
IMMPACT	Initiative on Methods, Measurement, and Pain Assessment in Clinical Trials
IMP	Investigational medicinal product
IRB	Institutional review board
MAR	Missing-at-random
MDMA	3,4-methylendioxy methamphetamine, ecstasy
MedDRA	Medical Dictionary for Regulatory Activities
MMRM	Mixed model for repeated measures
MNAR	Missing-not-at-random
NRS	Numerical rating scale
Omics	A generic term referring to analysis techniques like pharmacogenetics, genomics, epigenetics, transcriptomics, proteomics, metabolomics
PCS	Pain Catastrophizing Scale
PGIC	Patient Global Impression of Change
PGI-S	Patient Global Impression of Severity
PINP	Procollagen type I amino-terminal propeptide
PMI	Placebo multiple imputation
PMM	Pattern mixture model
PPT	Pressure pain threshold
PROMIS	Patient-Reported Outcomes Measurement Information System (PROMIS®)
PROMIS-29 profile	Patient-Reported Outcomes Measurement Information System (PROMIS®)-29 profile version 2.0
PROMIS-EDDEP39	Question EDDEP39 of the PROMIS Item Bank version 1.0 – Emotional Distress – Depression
PSEQ	Pain Self Efficacy Questionnaire
QTcF	Corrected QT interval (according to Fridericia's formula)
SAE	Serious adverse event
SF-MPQ-2	Short-Form McGill Pain Questionnaire 2
sIL-2R	Soluble interleukin-2 receptor
SOP	Standard operating procedure (used as synonym for all procedural documents)
TEAE	Treatment emergent adverse event
USP	United States Pharmacopeia
VAS	Visual analog scale
WPAI	Work Productivity and Activity Impairment

Système International d'Unités units and standard hematological and biochemical abbreviations are not listed.

## 3.2 Definition of terms

Term	Definition
Allocated subjects	Enrolled subjects who are assigned to IMP.
Applicable regulatory requirement(s)	Any law(s) and regulation(s) addressing the conduct of clinical trials of IMPs of the jurisdiction where the trial is conducted.
CRPS Type I	Occurs after a minor or major tissue injury without clinical signs of major peripheral nerve injury.
CRPS Type II	Occurs after an injury with clinical signs of major peripheral nerve injury.
End of the trial	The trial-related end of the trial is defined as the date of last subject out. The subject-related end of trial is defined as date of last contact with the subject according to the protocol.
Enrolled subjects	Subjects who signed an informed consent form.
Enrollment failures	Enrolled subjects who were not allocated to IMP.
First subject allocated	First subject that was allocated to IMP.
First subject in	Date of first enrolled subject.
Investigational medicinal product	A generic term describing the preparation(s) under investigation in this trial, i.e., neridronic acid and placebo.
Last subject out	Date of last contact with the last subject according to the protocol.
Patient	Person under a physician's care for a particular disease or condition.
Screened subjects	Screened subjects are subjects undergoing screening. Screening is any activity concerning subjects who could potentially be enrolled into the trial before the informed consent form is signed.
Subject	Individual who participates in a clinical trial (healthy person or patient), either as recipient of an IMP or as control.
Treated subjects	Subjects with at least 1 administration of IMP.

### Use of the terms “must” and “should”

When “must” is used, the action/item is always mandatory. Non-compliance with this instruction constitutes a protocol deviation.

When “should” is used, the action/item is recommended but not mandatory. Non-compliance with this instruction does not constitute a protocol deviation.

## 4 ETHICS

This trial will be conducted according to this protocol, the ethical principles that have their origin in the Declaration of Helsinki, good clinical practice (GCP), and applicable regulatory requirements.

This trial will be registered in public registries according to the applicable laws and requirements.

## **4.1 Independent ethics committees or institutional review boards**

The relevant independent ethics committees (IECs) or institutional review boards (IRBs) for this trial will be provided with all documents required to fulfill their responsibilities. Any updates thereof will be provided according to GCP and applicable regulatory requirements.

Trial activities will only start when approval from the relevant IECs or IRBs is available.

Documentation of all involved IECs or IRBs will be maintained according to GCP and applicable regulatory requirements.

